10.4	Response criteria	20
10.5	Statistical methods to be employed.....	22
10.6	Analysis plan.....	22
10.7	Trial supervision	22
11	Assessment of Safety	22
11.1	Definitions.....	22
11.2	Expected adverse drug reactions.....	23
11.3	Expected Serious Adverse Events	23
11.4	Recording and evaluation of adverse events.....	24
11.5	Reporting adverse events	24
11.6	Reporting of Suspected Unexpected Serious Adverse Reactions (SUSARs)....	24
12	Data handling and record keeping	25
13	Direct access to source data / documents.....	25
14	Publications policy	26
15	Finance	26
16	Ethical considerations.....	26
16.1	Consent	26
16.2	Ethical committee review	26
16.3	Declaration of Helsinki and ICH Good Clinical Practise	26
17	Regulatory approval	26
18	References	26
19	Appendix 1. Rationale for change of infusion regimen.	28

1 Study Synopsis

Title of clinical trial	A pilot study of thrombolysis during machine perfusion of circulatory death donor livers to prevent biliary strictures
Short title	Thrombolysis during machine perfusion of DCD donor livers
Sponsor name	Cambridge University Hospitals NHS Foundation Trust and the University of Cambridge
IRAS project number	297403
Sponsor number	A095973
Trial registry Reference number	ISRCTN
REC number	21//EE/0237
Medical condition or disease under investigation	Cholangiopathy in livers removed from donors following circulatory or brain death
Purpose of clinical trial	To assess whether a thrombolytic regimen during ex situ normothermic liver perfusion can prevent biliary strictures
Primary objective	To evaluate the safety and feasibility of adding fresh frozen plasma and TPA to the perfusate
Secondary objective (s)	Prevention of biliary strictures (cholangiopathy) Improved liver graft function
Study Design	Pilot study ascending dose three-arm randomised unblinded study
Study Endpoints	Bleeding intra-operatively Feasibility of treating livers with TPA. Return to theatre within 24 hours for bleeding Incidence of anastomotic and non-anastomotic strictures
Sample Size	60 liver recipients
Summary of eligibility criteria	Adults undergoing a deceased donor liver transplant from a donor after circulatory death
Investigational regimen	Tissue plasminogen activator (alteplase) with fresh frozen plasma added to the perfusate ex situ .
Route(s) of administration	Ex situ (ex vivo) into the perfusate of a liver undergoing ex situ perfusion
Maximum duration of treatment of a subject	The recipient is not treated, just the liver. Treatment of the liver lasts 60 minutes

2 General information

2.4 Laboratories / Technical departments

MRC Laboratory of Molecular Biology in Cambridge for RNA seq

2.5 Trial Manager

None

2.6 Committees attached to trial

None

2.7 Protocol amendments

2.7.1 Amendment 1, to address REC comments

Protocol 23/11/21. Version 2.0

- a) Addition of [name] as co-investigator
- b) Addition of a secondary endpoint: return to theatre for bleeding within 24 hours
- c) Alteration of a secondary endpoint from :
 “Total and post reperfusion intra-operative blood transfusion and blood loss”
 to:
 “Total and post reperfusion intra-operative blood transfusion (including cell saved blood”. Note that blood loss is already collected as an endpoint
- d) Addition of allergy to latex or gentamicin as exclusion criteria
- e) Alter the structure of the study in accord with the independent review to one of three ascending dose groups, 10, 20, and 50mg with each group containing a control liver with FFP and no TPA.

2.7.2 Amendment 2, to alter the perfusion protocol

Protocol 15/03/22, version 3.0

- a) Rate of infusion

Following receipt of evidence that the fibrin is present in livers before implantation, and not continuously throughout perfusion, the perfusion regimen has been changed to increase its efficacy in the first hour. Appendix 1 shows the evidence behind the change in perfusion regimen.

Perfusion regimen to change as follows: The initial bolus will be 20% TPA and FFP at the start of perfusion, with the remaining 80% given over the first 60 minutes

Group	TPA				FFP	
	TPA Bolus dose (mg)	Infusion dose (mg)	Infusion volume (mls)	Infusion rate (mls/hour)	Bolus volume (mls)	FFP infusion rate (mls/h)
A	2	8	8	8	50	200
B	4	16	16	16	50	200
C	10	40	40	40	50	200

- b) Inclusion of a separate cohort of DBD donor livers

A second group of 30 livers from donors after brain death will be included in the study

Other changes:

Version 3.1, date 21-04-22

Minor typographical errors corrected

Version 3.2, date 07-05-22

Alteration of protocol wording in respect of the changes in amendment one which were not completely reflected by the protocol change in versions 3.0 or 3.1.

2.7.3 Amendment 3, to alter perfusion protocol and add an additional site.

Protocol Version 4, date 18-07-22

- a) Addition of Newcastle Liver Transplant Unit at the Freeman hospital as a third site

- b) Alteration of infusion protocol

The current protocol involves 3 treatment groups, the first two of 5 alteplase treated liver transplants with a control, and the third group of 15 TPA treated liver transplants . This will change, and the third group will be divided into three group of TPA treated livers. One group will have 50mg alteplase infused as planned. Following this, D-dimer levels will be measured on perfusions in all groups. The lowest dose to achieve high D-dimer levels will then be chosen for the next two groups. These groups will include one where the infusions go into the reservoir and not directly into the arterial cannula, and one where the perfusion duration is stretched to 2 hours and not one. The table below gives the changes.

Group	TPA				FFP		Infusion Site
	TPA Bolus dose (mg)	Infusion dose (mg)	Infusion volume (mls)	Infusion rate (mgs/hour)	Bolus volume (mls)	FFP infusion rate (mls/h)	
A	2	8	8	8	50	200	Artery cannula
B	4	16	16	16	50	200	Artery cannula
C	10	40	40	40	50	200	Artery cannula
D	TBD				50	200	Reservoir
E	TBD				50	100	TBD

TBD: to be determined by D-dimer level comparisons.

Group D: dose to be determined, infused over 1 hour into the portal reservoir

Group E: Dose to be determined, infused over 2 hours either into the portal reservoir or hepatic artery cannula, depending on results of Group D.

Groups A, B, C and D will all get 50mls FFP bolus and 200mls infused over 1 hour, and Group E will get FFP infused over 2 hours as a source of plasminogen

2.7.4 Amendment 4. Change of Chief Investigator

Change of Chief investigator from [name] to [name]

2.7.5 Amendment 5 (declined)

Protocol version 5.1, dated 6/1/23

Added provision to consent retrospectively if the liver is treated following consent and the recipient subsequently changed to a recipient who has not yet been approached about the study. This amendment did not receive a favourable opinion as submitted and the protocol was revised and a separate consent form produced.

2.7.6 Amendment 5 (modified and resubmitted) dated 08/02/2023

Protocol version 5.1, dated 07/02/23

- a) Amendment to provide more detailed guidance on what to do if liver is treated, then reallocated.
- b) Consent forms for patients being offered a liver that has already been treated.
- c) An amendment to protocol in view of fact that 10mg dose given over 60 minutes appears to be efficacious, so 50 mg group (group C) will not be undertaken. 10mg dose will be used for group D.

2.8 Abbreviations

°C	degrees Celsius
ALT	Alanine transaminase
AST	Aspartate transaminase
CTIMP	Clinical trial of an investigational medicinal product
DBD	Donation after brain death
DCD	Donation after circulatory death
EU	European Union
FFP	Fresh frozen plasma
GCP	Good clinical practice
H&E	Haematoxylin and eosin, a histology stain
ICH	International Conference on Harmonisation
ICJME	International Committee of Medical Journal Editors
INR	International normalised ratio
MEAF	Model for early allograft function
MHRA	Medicines and healthcare products regulatory agency
mls	millilitres
MRCP	magnetic resonance cholangiopancreatography
MSB	Martius Scarlet Blue, a histology stain
NaHCO ₃	Sodium bicarbonate
NAS	Non anastomotic biliary strictures
NESLiP	Normothermic ex situ liver perfusion
NHSBT	National Health Service Blood and Transplant
NMP	Normothermic machine perfusion
pH	$-\text{Log}_{10} [\text{H}^+]$
REC	Research ethics committee
RIFLE	Risk, Injury, Failure, Loss, and End-stage kidney disease
RNA	Ribonucleic acid
SmPC	Summary of Product Characteristics
SUSAR	Suspected unexpected serious adverse reactions
TPA	Tissue plasminogen activator
UK	United Kingdom

2.9 Trial summary

Livers from donors donating after circulatory arrest (DCD donors) are associated with a high incidence of bile duct strictures after transplantation. This remains the case for liver subject to *ex situ* normothermic perfusion (NESLiP) prior to transplantation, with a rate of around 20% for anastomotic and non-anastomotic strictures. Livers from brain dead donors have a lower incidence of strictures after NESLiP at around is 8%, but they are equally disabling. Recent work in Cambridge has shown that DCD livers during NESLiP develop infarcts in the stromal walls of bile ducts in association with fibrin plugs in the peri-biliary blood supply, suggesting that these fibrin plugs may be the cause of the stromal infarcts, and by extrapolation the bile duct strictures. Subsequent work has shown that by using a similar thrombolytic protocol with tissue plasminogen activator (TPA, alteplase) to that used for clearing clots from the coronary circulation in patients having heart attacks results in no visible fibrin plugs and no bile duct necrosis.

In this study livers will undergo NESLiP and receive an infusion of TPA using a standard thrombolytic regimen for the first 60 minutes of perfusion, with a minimum perfusion time of 2 hours. Alteplase has a half-life of 5 minutes *in vivo* and a 1 hour perfusion will mean there will be at least 60 minutes between the end of the TPA infusion and removing the liver from the machine. Not all DCD donor livers will be viable on testing during NESLiP, but experience suggests that two thirds will meet the viability criteria and be transplanted. It is unlikely that there will be any active TPA in the circuit at the point of removal from the machine. Recipients will then undergo standard follow up with no further research intervention.

This study is a pilot study of 30 DCD and 30 DBD transplants to assess the safety of thrombolysis during *ex situ* perfusion, and to give an idea of its effects on the subsequent outcome of the implanted liver with particular reference to early function and bile duct strictures. The results will be compared with recipients randomised to receive FFP and no TPA. If the study suggests that the intervention is safe and efficacious the protocol will be used in a larger scale multicentre study.

3 Study Flow Chart

Donor liver placed on OrganOx *metra* machine

[figure not shown]

Figure 1: Flow chart for NESLiP assessment of donor livers

4 Background

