5.4 Sample size determination

Previous experience with back-to-base perfusion of DCD livers has been associated with a 20% incidence of anastomotic strictures and a 20% incidence of non-anastomotic bile duct strictures (unreported Cambridge data). In a cohort of 20 patients receiving a DCD liver treated by NESLiP it is likely that one will die, five will undergo retransplantation and four will develop non-anastomotic strictures. Similarly, the incidence of non-anastomotic strictures in DBD livers undergoing NESLiP in Cambridge is 8%, with a further 15% suffering anastomotic strictures.

A sample size of 30 DBD and 30 DCD should allow us to evaluate the safety of this therapy. It may also help determine whether the thrombolytic regimen increases the proportion of perfused livers that get transplanted and abolishes non-anastomotic strictures, and therefore whether it is worth proceeding to a formal randomised study and how to power that study

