5.6 Study endpoints

5.6.1 *Primary endpoint*

- Post reperfusion intra-operative blood loss
- Feasibility of adding TPA and FFP to livers undergoing normothermic perfusion before transplantation

5.6.2 *Secondary endpoint*

- Return to theatre in first 24 hours for bleeding
- Total and post reperfusion intra-operative blood transfusion
- Liver utilisation: proportion of liver perfusions resulting in a transplant
- Incidence of symptomatic anastomotic and non-anastomotic strictures at 6 months post-transplant
- Incidence of any anastomotic or non-anastomotic stricture excluding those related to hepatic artery thrombosis
- Incidence of “clinically relevant” non-anastomotic strictures, using the van Rijn definition¹¹
- Incidence of post reperfusion syndrome: 30% fall in mean BP lasting at least a minute in the first 5 minutes post reperfusion or the need for adrenaline or doubling of noradrenaline to support the circulation.
- Early allograft function (Olthoff criteria¹² and MEAF score¹³)
- Incidence of hepatic artery thrombosis in the first 6 months
- Incidence of acute kidney injury (RIFLE criteria)
- D-dimer release into perfusate compared to controls

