8.1 Liver perfusate

The OrganOx perfusate will be the same as routinely used in the centre, and will comprise 3 units of packed red cells, a plasma substitute (human albumin in Cambridge, Gelofusine at the Royal Free) together with the standard additives and infusions.

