10.3 Sample size considerations

This is a pilot study of the safety and efficacy of *ex situ* thrombolytic therapy to assess whether a full clinical trial of the treatment is warranted. The TPA perfused livers and the number of transplants will be compared to the control perfusions .

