10.4.4 Acute kidney injury

Acute kidney injury will be defined by the RIFLE criteria as a creatinine in the first 7 days post-transplant which has risen more than two-fold higher than the pre-transplant value, or the need for haemofiltration or dialysis. The peak to baseline values will also be compared.

The ratio of peak (d1-7) over baseline creatinine will also be recorded and compared with historical comparators; the absolute percentage where the ratio is ≥ 2.0 will also be compared.

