10.6 Analysis plan

Transplant recipients in the pilot study will be compared with twice the number of recipients of DCD livers that were machine perfused in the recipient centres in the previous 2 years. They will be matched for agonal phase duration, cold ischaemia time and UK donor liver index ¹⁶.

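### Sections 2.9 and 10.6 name different comparators and neither is ranked; as worded, 10.6 also leaves FFP-only controls on the intervention side and DBD recipients without a like-for-like historical group

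*Protocol*

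**What the plan says.** Three places in the protocol point to a concurrent control group. Section 2.9, directly after describing the pilot's interest in safety, early function and strictures, states: "The results will be compared with recipients randomised to receive FFP and no TPA". Section 10.3 states: "The TPA perfused livers and the number of transplants will be compared to the control perfusions". One secondary endpoint in section 5.6 is "D-dimer release into perfusate compared to controls". Section 7 supplies those controls by allocating one transplant in six, in every arm, to plasma without TPA.

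Two places point to history. Section 10.6 states: "Transplant recipients in the pilot study will be compared with twice the number of recipients of DCD livers", drawn from machine perfusions at the recipient centres over the preceding two years. It adds: "They will be matched for agonal phase duration, cold ischaemia time and UK donor liver index". Section 10.6 does not mention the randomised controls. Section 10.4.4 says the peak-to-baseline creatinine ratio will be "compared with historical comparators".

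Section 10.4.3 refers only to treatment and comparator groups, without saying who the comparators are. Section 5.1 describes the study as open label, and section 10.1 gives the analysis to a member of the research team.

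**The concern.** The two comparisons answer different questions. On the randomised side both groups receive FFP, so the contrast isolates TPA. On the historical side, section 8.1 says "The OrganOx perfusate will be the same as routinely used in the centre", which means red cells with albumin or Gelofusine; FFP is a study addition under 8.2. The historical contrast therefore measures TPA, FFP and calendar period together. For post-reperfusion blood loss, a primary endpoint, the two could disagree. With no ranking and no blinding, the choice between them could be made after the results are seen.

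Two further problems lie in the wording of 10.6. Its intervention side is not limited to recipients of TPA-treated livers, so the randomised controls are pooled with them unless the analyst decides otherwise. Its historical cohort is DCD only, although half of the planned recipients receive DBD livers.

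**Working it through.** **1. The plan's own figure.** Sections 5.3 and 10.2 expect about 45 DCD and 35 DBD perfusions for 30 transplants of each type. With non-viability of one third and 15% (5.3): 30 / (2/3) = 45.0 and 30 / 0.85 = 35.3. Both reproduce. The protocol states no alpha or power.

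**2. Number of controls.** Section 7 gives one in six: 60 / 6 = 10 FFP-only and 50 TPA recipients. An even split by donor type (an assumption) gives 5 FFP-only and 25 TPA among the 30 DCD recipients. The count is approximate. Section 4.7 says at least one control per group of six, and group C is cancelled. Four remaining groups of six in each donor type would give 48 recipients and 48 / 6 = 8 controls, although 10.2 still states 60.

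**3. Which denominator applies to 10.6.** The historical cohort is DCD, so the relevant pilot group is the 30 DCD recipients. Two historical recipients for each gives 30 v 60. Limited to TPA recipients, it is 25 v 50.

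**4. Effect of pooling.** Let p be the TPA stricture rate and q the FFP-only rate. The pooled rate is (25p + 5q) / 30. Take a historical rate of 20% (non-anastomotic strictures in DCD livers, 5.4) and q = 20%:

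| p | Pooled rate | Difference from 20%, pooled | Difference, TPA only |
|---|---|---|---|
| 0% | 3.3% | 16.7 points | 20 points |
| 5% | 7.5% | 12.5 points | 15 points |
| 10% | 11.7% | 8.3 points | 10 points |

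Each difference shrinks by one sixth. That depends on q equalling the historical rate. With p = 0%, q = 0% gives no shrinkage (20 points), and q = 40% gives a pooled rate of 5 × 0.40 / 30 = 6.7% and a difference of 13.3 points.

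**5. Illustrative power.** This uses exact enumeration of Fisher's test (the test named in 10.5) at an assumed two-sided 0.05, with historical and FFP-only rates of 20%, ignoring matching:

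| p | Historical, controls pooled (30 v 60) | Historical, TPA only (25 v 50) | Randomised DCD (25 v 5) |
|---|---|---|---|
| 0% | 52% | 81% | 26% |
| 5% | 25% | 34% | 11% |
| 10% | 11% | 13% | 6% |

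The p = 0% row is the scenario in 5.4 in which non-anastomotic strictures are abolished. Keeping 60 historical recipients against 25 TPA recipients gives 79%, so the loss comes from pooling and not from cohort size. The last column shows how differently the two comparisons are resourced.

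**6. DBD recipients.** Matching in 10.6 includes the agonal phase. Section 4.1 describes an interval between withdrawal of treatment and circulatory arrest for DCD donors only; DBD donors reach theatre ventilated with the heart beating. No historical DBD group is named anywhere, so 30 of 60 recipients are either left out of 10.6 or set against livers of another type.

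**The case against.** A pilot may properly use both a small randomised control group and a larger historical one. Section 10.6 lists no outcomes, and 10.4.4, the only outcome tied explicitly to history, is worded as an addition. A reader might infer that the protocol assigns two comparators to the same list of outcomes. It does not go that far; the overlap comes from the general wording of 2.9 and 10.6. What stands is that each section presents its comparison alone and none is ranked.

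A reader might also infer that the protocol classes FFP-only recipients as treated. It never says so, and 10.3 and 10.4.3 show that it distinguishes the groups. The intent of 10.6 may well have been TPA recipients only. What stands is that its literal wording includes everyone and excludes nobody.

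A third tempting step is to read section 5.4, "A sample size of 30 DBD and 30 DCD should allow us to evaluate the safety of this therapy", as a claim that testing against about ten controls would establish safety. The protocol states no alpha, power or non-inferiority margin and presents the study as groundwork for a larger trial. No fault is raised against 5.4.

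The historical contrast is not meaningless either. The synopsis objective and the feasibility endpoint concern FFP and TPA together, so comparison with routine perfusate bears on the declared package. Confounding by period remains. Finally, a statistical analysis plan, which was not available, could rank the comparisons, and the opening of 10.4 before 10.4.2 could not be consulted. Neither removes the conflict already in the protocol text.

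**Conclusion.** The point holds in this form. Sections 2.9 and 10.3 conflict with 10.6 and 10.4.4 on the comparator and nothing ranks them. As worded, 10.6 includes the FFP-only recipients and gives the DBD recipients no matched historical group.

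The dilution concerns about 5 of 30 DCD recipients. It would be tempting to quote 10 of 60, but 10.6 is a DCD comparison. The one-sixth shrinkage assumes an even split of controls by donor type and FFP-only outcomes equal to historical ones. The concern that FFP and period matter is itself a reason why that equality may fail, so one sixth is a conditional figure. The power values further assume two-sided 0.05 and unmatched data, and they illustrate strictures, a secondary endpoint. They say nothing about power for blood loss.

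**What to change.** Reword section 10.6 as follows.

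- **Main comparison.** Name TPA plus FFP versus FFP alone, as randomised, for blood loss and the other clinical endpoints. Pool controls across groups, take donor type into account, and report differences with 95% confidence intervals alongside the tests in 10.5.
- **Supportive comparison.** Limit the historical contrast to recipients of TPA-treated livers. Match within donor type, with variables that exist for DBD donors, or state that it applies to DCD only.
- **Check on FFP and period.** Show FFP-only recipients against the historical group separately.
- **Alignment.** Bring 10.4.4 into line, so that the creatinine ratio is first compared with the randomised controls.

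This is amendment wording only. It changes no treatment, procedure or recruitment target. The price is imprecision: the main contrast rests on about 8 to 10 controls, roughly 4 or 5 per donor type, so conclusions will be modest. Pooling controls across successive groups also carries some drift over time and infusion method, which the report should acknowledge.

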4.1 Introduction

There are two sorts of deceased organ donors, those certified dead by brain stem criteria (DBD donors) and those certified dead by circulatory criteria (DCD donors). Brain dead donors are confirmed dead and brought to the operating theatre for organ removal while still on a ventilator. The heart is still beating and there is still a blood supply to the organs up to the point they are cooled *in situ* and removed. Circulatory death donors, on the other hand, usually have some sort of brain catastrophe but do not fulfil criteria for brain stem death, but nevertheless future treatment is considered futile and not in their interests. The patients have their treatment withdrawn, ventilation stopped, and after a period of minutes to hours the circulation stops. Death is verified after 5 minutes of circulatory arrest, after which the donor is brought around to the operating theatre, the organs are flushed *in situ* and then removed. Hence there is a period of many minutes where the organs are warm but without a blood supply, a state termed warm ischaemia.

In the UK in 2019/20 there were 1580 deceased organ donors, two thirds of which were DBD and a third DCD¹. Livers were used from 76% of DBD donors and only 27% of DCD donors, largely because of uncertainty regarding the effects of the period of warm ischaemia. DCD donor livers have a higher incidence of never working (primary non function, 4%), more initial poor function (around 30%)², and a high incidence of bile duct strictures (scarring of the bile ducts in over 20%)², compared to DBD (6-8%). DCD liver recipients also experience more acute kidney injury than recipients of DBD livers³.

The aetiology of bile duct strictures in donor livers has not been clear but has been thought to be related to clots in the small vessels supplying the bile ducts (the peri-biliary plexus), since the appearance is similar to that seen when the arterial supply to the liver is lost. The peri-biliary thrombi have been assumed to form during the period of hypoperfusion and circulatory arrest, but this is unlikely since they occur in settings where the donor is heparinised before withdrawal of treatment (such as occurs in Belgium).

Recent research with kidneys undergoing normothermic perfusion has shown the upregulation of fibrinogen genes with ischaemia, and the development of fibrin plugs in small vessels of the kidney, which respond to thrombolytic treatment⁴. At the same time, we have demonstrated that DCD livers undergoing NESLiP develop infarcts of the bile duct wall in association with plugs of fibrin in the peribiliary plexus (figure 2), and that treatment with TPA while using fresh frozen plasma as a source of plasminogen, is associated with an absence of such fibrin plugs and no stromal necrosis.

TPA is used clinically to treat thrombotic occlusions of the coronary and cerebral arteries in patients experiencing heart attacks and strokes, respectively. In these settings it known to clear thrombi and restore a circulation. TPA has also been instilled into the hepatic artery of livers undergoing transplantation while the liver is being implanted. Although reported to be effective at reducing cholangiopathy this strategy has also been associated with excess bleeding⁵. The ability to treat livers *ex situ* before implantation affords a safer opportunity for treatment.

[figure not shown]

Figure 2: H&E and MSB stained sections of bile ducts from two separate livers showing patchy necrosis of the duct and intravascular clumps of fibrin and erythrocytes. There is widespread stromal necrosis and epithelial loss visible in all 4 panels, best appreciated on the H&E sections. In section (a) eosinophilic inclusions are present in the subendothelial vessels (arrowed). In section (b) these same subendothelial areas are now seen to be intravascular aggregates of fibrin and erythrocytes (staining red and yellow with Martius Scarlet Blue, MSB). The same phenomenon is seen in sections (c) and (d) from a different liver.

